Research Protocol

General Information

Protocol Title: Acute Effects of Cannabigerol

Protocol Number: NCT05257044

Protocol Registration Location and Date: clinicaltrials.gov (25/02/2022)

Document Date: August 10, 2024

Project Summary

Cannabigerol (CBG) is a phytocannabinoid increasing in popularity, with preclinical research indicating it has anxiolytic and antidepressant effects. However, there are no published clinical trials to corroborate these findings in humans. Therefore, the primary objective of this study is to examine the acute effects of CBG on anxiety, stress, and mood. Secondary objectives are to examine whether CBG produces subjective drug effects or motor and cognitive impairments. We will assess these objectives using a double-blind, placebo-controlled cross-over field trial with 34 healthy adult participants with experience using cannabis. Participants will complete two sessions (with a one-week washout period) via Zoom. In each, they will provide ratings of anxiety, stress, mood, and subjective drug effects prior to double-blind administration of 20mg hemp derived CBG or placebo tincture (T0). These ratings will be collected again after participants orally ingest the product and complete an online survey (T1), again after they complete the Trier Social Stress Test (T2), and again after they complete a verbal memory test and the DRUID impairment app (T3). We hypothesize that CBG will decrease anxiety, decrease stress, and elevate mood. Further, we hypothesize that ratings of subjective drug effects will be low and that CBG will not produce motor or cognitive impairments.

Rationale and Background

The rapid proliferation of the new legal cannabis market has instigated producers to cultivate an array of novel products to satisfy consumers' growing interest. While products high in delta-9-tetrahydrocannabinol (THC) continue to saturate the market [1], a growing body of consumers are seeking alternative non-intoxicating products carrying the promise of easing what ails them. Producers are responding to this demand by isolating various minor phytocannabinoids and marketing them with bold, but largely unsubstantiated, claims of their therapeutic potential. While cannabidiol (CBD) continues to be the dominant non-intoxicating cannabinoid of interest to both consumers and researchers, cannabigerol (CBG) is rapidly increasing in popularity [2].

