After completing three baseline trials of the DRUID app participants will schedule their testing sessions. The PI or RA will assign their ID code (sequentially) and will provide the participant with contact information of a CBG producer who will ship color-coded vials of hemp derived CBG and placebo directly to them. Finally, participants will be instructed to abstain from using any cannabis products including CBG for a minimum of 24 hours prior to their testing session.

Testing Sessions: Approximately one-week after the pre-testing Zoom session, participants will meet with a RA (blinded to the color-codes used for the drug and placebo) on Zoom for their first testing session. First, the RA will confirm that participant has abstained from use of cannabis or CBG for a minimum of 24 hours prior to the testing session. As depicted in Figure 1, participants will then provide baseline (T0) ratings of their subjective state (anxiety, stress, mood). Specifically, participants will rate their subjective levels of anxiety and stress using 0 (not at all) to 10 (extremely) visual analogue scales, and they will rate their subjective mood using a 0 (extremely negative) to 10 (extremely positive) visual analogue scale. They will also complete the state form of the State-Trait Anxiety Inventory, which assesses symptoms of anxiety participants are experiencing in the moment [12].

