To examine the acute effects of CBG on verbal memory, a 2 x 5 repeated-measures analysis of covariance (ANCOVA) will be conducted with condition (CBG, placebo), and CVLT-II trial (Trial 1, Trial 2, Trial 3, Trial 1B, Short-Delay) as within-subjects factors, order of drug administration as a covariate, and number of words correctly recalled as dependent variable.

Finally, to assess the effects of CBG vs. placebo on impairment, a one-way repeated measures ANCOVAs will be conducted to compare DRUID scores at baseline, in the CBG condition, and in the placebo condition, while controlling for order.

Expected Outcomes

CBG is increasing in popularity, with many individuals claiming this non-intoxicating legal substance has medicinal properties and effectively reduces anxiety, depression, pain, and symptoms of other medical conditions. While a small body of pre-clinical rodent studies support these claims currently no objective human research on the potentially beneficial or detrimental effects of CBG exists. As such, this will be the first objective examination of the potentially beneficial and detrimental effects of CBG on humans. Results will help to inform current and potentially future CBG users on its potential risks and benefits.

Dissemination of Results

Results will be disseminated at scientific conferences (e.g., International Cannabinoid Research Society, Gordon Research Conference) and in a scientific journal (<https://www.nature.com/articles/s41598-024-66879-0>). A press release will be issued by the PI's university following publication. [name] will be first author, [name] will be second author, [name] will be third author, and [name] will be last author.

Duration of the Project

Recruitment, testing, data entry, data analysis, and preparation of the manuscript are anticipated to require 2 years.

Problems Anticipated

There are no anticipated problems.

Project Management

[name] will train research assistants, oversee data collection, check the data for data entry errors, analyze the data, and prepare the manuscript.

[name] will advertise the study, helped collect and enter data, helped interpret the results, and help prepare the manuscript.

[name] and [name] assisted [name] in designing the study and will help prepare the manuscript.

Ethics

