sized statistically significant main effect of time, $F(2, 64) = 8.20, p < .001, \eta^2 = .204$, and a small-sized main effect of condition that was not statistically significant, $F(1, 32) = 1.19, p = .283, \eta^2 = .036$. This main effect of time was qualified by a moderately large-sized statistically significant interaction between condition and time, $F(2, 64) = 4.90, p = .011, \eta^2 = .133$. Probing of this interaction revealed a moderately large-sized simple effect of condition on change in subjective stress ratings at T1, $F(1, 32) = 5.02, p = .032, \eta^2 = .136$. In contrast, there were no significant differences in changes in stress ratings in the CBG and placebo conditions at T2, $F(1, 32) = 0.31, p = .583, \eta^2 = .010$, or T3, $F(1, 32) = 2.26, p = .142, \eta^2 = .066$.

The 2 x 3 repeated measures ANCOVA on changes in subjective mood ratings revealed no significant main effects of time, $F(2, 64) = 2.56, p = .085, \eta^2 = .074$, or condition, $F(1, 32) = 3.25, p = .081, \eta^2 = .092$, and no condition x time interaction, $F(2, 64) = 2.27, p = .111, \eta^2 = .066$.

Verbal Memory

A 2 x 5 repeated measures ANOVA with condition (CBG, placebo) and trial as within-subjects factors and order as a covariate revealed a moderate-sized effect of condition that was statistically significant, $F(1, 30) = 4.17, p = .050, \eta^2 = .122$ and a large-sized effect of time that was statistically significant, $F(4, 120) = 70.14, p < .001, \eta^2 = .700$. The interaction between condition and time was small and not statistically significant, $F(4, 120) = 0.38, p = .820, \eta^2 = .013$. Verbal memory test performance was significantly better in the CBG condition.

DRUID Impairment

The one-way repeated measures ANCOVA on DRUID impairment scores revealed a small sized effect of condition that was not statistically significant, $F(2, 64) = 0.76, p = .474, \eta^2 = .023$.

Complete results can be found in the published manuscript:

<https://www.nature.com/articles/s41598-024-66879-0>

References

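### The DRUID analysis asks a CBG-versus-placebo question but tests it with a three-level F that includes a non-comparable pre-testing baseline, and no CBG-placebo contrast or confidence interval is planned

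*Combined protocol and SAP*

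**What the plan says.** The Project Summary states a null hypothesis for impairment: "we hypothesize that ratings of subjective drug effects will be low and that CBG will not produce motor or cognitive impairments". The Secondary Outcomes part of the Data Analysis Plan introduces the DRUID analysis as one "to assess the effects of CBG vs. placebo on impairment", but what it plans is this: "a one-way repeated measures ANCOVAs will be conducted to compare DRUID scores at baseline, in the CBG condition, and in the placebo condition", with order controlled for. No CBG-placebo contrast, confidence interval or decision rule for DRUID is given.

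The DRUID baseline belongs to the Pre-testing Session. Participants download the app and complete the baseline trials there; then, "After completing three baseline trials of the DRUID app participants will schedule their testing sessions". The first testing session follows about a week later. The abstinence instruction comes after those trials and concerns the testing sessions: "participants will be instructed to abstain from using any cannabis products including CBG for a minimum of 24 hours prior". The research assistant's abstinence check is described only for the testing sessions. On-treatment DRUID runs come late in each testing session, after the vial, the Trier Social Stress Test and the CVLT-II.

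Under DRUID Impairment, the Results section says: "The one-way repeated measures ANCOVA on DRUID impairment scores revealed a small sized effect of condition that was not statistically significant", with F(2, 64) = 0.76, p = .474 and an eta-squared of .023. No CBG-placebo difference or interval is given.

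**The concern.** The test does not match its question. A 2-df F over baseline, CBG and placebo can be significant because baseline differs from both treated sessions while CBG and placebo are identical. Baseline is exposed to exactly that. It is always first, it precedes any product and any stressor, and abstinence is not described as required or checked at that visit, although past-month cannabis use is an entry criterion. The order covariate separates CBG-first from placebo-first participants. It cannot remove a position effect that everyone shares.

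The opposite result is no easier to interpret. Because the hypothesis is that impairment is absent, a reader will look to the DRUID result for support. A non-significant omnibus F says little about how large a CBG-placebo difference remains possible. This is the trial's motor and cognitive impairment score, and under Expected Outcomes the results are meant to inform CBG users about risks as well as benefits.

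**Working it through.** **Inputs.** N = 34, power .80, d = 0.50 and alpha .05 (Power). Reported F(2, 64) = 0.76 (Results, DRUID Impairment). The documents give no DRUID means or SDs, so effects are in units of the SD of a paired difference, sphericity is assumed, and the baseline shifts are assumptions.

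**1. The plan's own sample size.** A two-sided paired t-test at .05 with d = 0.50 needs N = 34 (power .808; N = 33 gives .795). With one further df spent on order (32 error df), power is .807. So the stated N fits a 1-df paired comparison, which is the contrast the DRUID plan leaves out.

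**2. The reported F is internally consistent.** Eta-squared = (2 × 0.76)/(2 × 0.76 + 64) = 1.52/65.52 = .023. Error df = 2 × (34 − 2) = 64. F = 0.76 gives p = .472; an unrounded F of 0.755 gives .474.

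**3. Rejection when CBG equals placebo.** Noncentrality λ = 2n Σ(μ − μ̄)², referred to F(2, 64). If only baseline is shifted, by b, then Σ(μ − μ̄)² = 2b²/3 and λ = 4 × 34 × b²/3 = 45.33b².

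| Baseline shift b | λ | P(F significant) |
|---|---|---|
| 0.1 | 0.45 | 8% |
| 0.2 | 1.81 | 20% |
| 0.3 | 4.08 | 41% |
| 0.5 | 11.33 | 85% |

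The direct CBG-placebo contrast rejects 5% of the time in every row.

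**4. Power for a true CBG-placebo difference of 0.5.**

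| Test | λ | Power |
|---|---|---|
| F(2, 64), baseline midway | 8.5 | 0.72 |
| F(2, 64), baseline equal to CBG or to placebo | 11.33 | 0.85 |
| F(2, 64), baseline 0.25 outside the pair | 19.83 | 0.98 |
| Direct contrast, F(1, 32) | 34 × 0.25 = 8.5 | 0.81 |

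**5. What the reported F leaves open.** For a given CBG-placebo difference δ, the between-condition sum of squares is smallest when baseline lies midway, where Σ(m − m̄)² = δ²/2 and F = nδ²/2. Hence |δ| ≤ √(2F/n) = √(1.52/34) = 0.21. The 95% half-width on 32 df is 2.037/√34 = 0.35. The interval could therefore reach 0.21 + 0.35 = 0.56, above the planned 0.50. This takes the reported F as comparing means averaged over the two orders.

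**6. Power to exclude a margin.** One-sided .05, true difference zero, n = 34, 32 df: 0.89, 0.74, 0.53 and 0.31 for margins of 0.5, 0.4, 0.3 and 0.2 SD. The documents state no margin.

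**The case against.** Several points on the other side stand, and they limit what can be claimed.

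- **Participants were intoxicated at baseline.** A reader might infer this. The documents show only that abstinence was not described as required or verified at pre-testing. Nor do they give the size of any practice effect, which three baseline trials may reduce. At a shift of 0.1 the excess rejection is small.
- **The three-level F loses power.** This is tempting but not general. The 0.72 is the worst case; when baseline equals either condition or lies outside the pair, the F has more power than the direct contrast.
- **The F causes real impairment to be missed.** For a true difference of 0.3 the direct contrast itself has power 0.40, so it misses about 60% of the time. That reflects n = 34, not the choice of F.
- **The trial declares CBG free of impairment.** The Project Summary states a hypothesis, and the Results section says only that the effect was small and not significant. No conclusion of absence appears.
- **Cognition rests wholly on a null result.** The CVLT-II analysis already has a two-level CBG/placebo factor, and its reported condition effect, F(1, 30) = 4.17, p = .050, favoured CBG.
- **The false positive did not happen.** The DRUID F was 0.76. A practice effect that made baseline the worst score would also be visible in the means.

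The mismatch between question and test survives all of these, as does the lack of any interval for the comparison of interest.

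**Conclusion.** The point holds in this form. Followed exactly, the DRUID plan answers whether three occasions differ, one of them non-comparable by design, rather than whether CBG differs from placebo. The cost is mainly specificity: 8% to 85% rejection with no drug effect, for assumed baseline shifts of 0.1 to 0.5 SD. For the reported data, the live issue is that a non-significant F cannot support "CBG will not produce motor or cognitive impairments". On the information given, a CBG-placebo difference of about 0.56 SD of the paired difference might not be excluded. That is an upper bound, not an estimate; the actual interval may be tighter. The confounding of baseline with session follows from the schedule and needs no assumption. The figures rest on sphericity and on shifts that the documents do not supply. DRUID is a secondary outcome and the correction is cheap, so this should be fixed but does not threaten the primary analysis.

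**What to change.** 1. Make the DRUID test the 1-df CBG-minus-placebo contrast, adjusted for order/period, with its 95% CI in score units.
2. Show the pre-testing baseline descriptively only, and state how its three trials are combined into one score.
3. Report this contrast and CI alongside the existing F(2, 64), labelled as added after the results were known.
4. Do not describe a non-significant result as absence of impairment; say what the CI excludes. If a margin is used, justify it in score units and disclose that it is post hoc for these data. A margin is optional; the contrast and CI are not.
5. For CVLT-II the condition effect is already the right 1-df test, so only its CI needs adding.

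The cost is a change of wording and one contrast from data in hand. The downside is that the DRUID conclusion may become inconclusive, especially against margins below 0.5 SD.

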Data Analysis Plan: Pairwise deletion will be used to handle the small amount of missing data anticipated. Alpha will be set to .05 and effect sizes of 0.01 will be interpreted as small, 0.06 will be considered medium, and 0.14 and above will be considered large. Data will be analyzed using IBM SPSS v.27.

Percentages, means, and standard deviations will be used to determine the demographic characteristics and cannabis use patterns of the sample. Mean DASS subscale scores, mean subjective state (mood, anxiety, stress) ratings, mean STAI state and trait anxiety scores, and mean

subjective drug effect ratings will be computed at baseline (T0) for each condition.

Change scores will be created by subtracting baseline (T0) scores from T1, T2, and T3 scores for the subjective state ratings (anxiety, stress, mood), STAI state anxiety scores, and subjective drug effect ratings (dry eyes, dry mouth, sleepiness, appetite, heart palpitations/racing heart).

Primary Outcomes: To assess the primary outcome (determine the effects of CBG vs. placebo on anxiety, stress, and mood) a series of 2 x 3 repeated-measures ANCOVAs will be conducted with condition (CBG, placebo), and time (T1, T2, T3) as within-subjects factors, order of drug administration as a covariate, and changes (difference from T0 to T1, T2, T3) in ratings of anxiety, stress, and mood as separate dependent variables.

Secondary Outcomes: To assess the effects of CBG on subjective drug effect ratings (dry eyes, dry mouth, sleepiness, appetite, heart palpitations/racing heart) a series of 2 x 3 repeated-measures ANCOVAs will be conducted with condition (CBG, placebo), and time (T1, T2, T3) as within-subjects factors, order of drug administration as a covariate, and changes (difference from T0 to T1, T2, T3) in these subjective drug effect ratings as the dependent variables.

To determine the effects of CBG vs. placebo on intoxication, drug effect, and drug liking ratings a series of 2 x 3 repeated-measures ANCOVAs will be conducted with condition (CBG, placebo), and time (T1, T2, T3) as within-subjects factors, order of drug administration as a covariate, and ratings of each indicator of drug effects as the dependent variables.

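### Stress and mood results carry no direction, and the five stress F values imply either a CBG–placebo difference that changes sign over time or tests that do not estimate the order-averaged effect

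*Combined protocol and SAP*

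**What the plan says.** The Project Summary sets the primary hypotheses with a direction: "We hypothesize that CBG will decrease anxiety, decrease stress, and elevate mood".

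The Data Analysis Plan tests them with 2 x 3 repeated-measures ANCOVAs on change from T0, with order of administration as a covariate, in SPSS. It does not state how order is coded or at what value of order the effects are tested. The condition means it lists are baseline ones ("subjective drug effect ratings will be computed at baseline (T0) for each condition"). It specifies no signed CBG minus placebo estimate and no confidence interval.

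In Results (Primary Outcomes), under Subjective Anxiety, Stress, Mood, the stress analysis has "and a small-sized main effect of condition that was not statistically significant", with "F(1, 32) = 1.19, p = .283", and an interaction with "F(2, 64) = 4.90, p = .011". Then: "Probing of this interaction revealed a moderately large-sized simple effect of condition on change in subjective stress ratings at T1", with "F(1, 32) = 5.02, p = .032". It continues: "In contrast, there were no significant differences in changes in stress ratings in the CBG and placebo conditions at T2" (F = 0.31) or at T3 (F = 2.26). No mean or sign is attached to any of these. Mood is reported in the same way, with no significant effect. For anxiety and for verbal memory the text does state the direction.

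**The concern.** An F test has no sign. A directional hypothesis about stress cannot be judged from a significant F at T1 alone, and the overall condition effect on stress is not significant. Two of the three primary outcomes therefore lack the one fact that the hypothesis needs.

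For stress, the missing sign also matters to how the numbers fit together. T1 precedes the Trier Social Stress Test and T2 follows it. Whether the CBG–placebo difference kept its direction across the stressor is central to interpreting the outcome. The printed F values do not fit the simplest picture, a difference of constant direction and varying size, unless the tests refer to something other than the average over the two orders. In that case the printed p values do not answer the question a reader takes them to answer. The same model is planned for anxiety and mood, so the question about order coding applies to them too.

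**Working it through.** **Inputs** (Results, stress paragraph): simple effects F = 5.02 (T1), 0.31 (T2), 2.26 (T3), each on 1 and 32 df; condition F(1, 32) = 1.19; condition by time F(2, 64) = 4.90. With 34 people and one covariate, 34 − 2 = 32 df, as printed. A 17/17 split by order is assumed from the odd/even allocation.

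**Reproducing the printed figures.** From F and df: condition p = .2835, eta-squared .036; interaction p = .0105, .133; T1 p = .032, .136; T2 p = .582, .010; T3 p = .143, .066. The printed .583 and .142 lie within the rounding of F. Each F agrees with its own p and eta-squared, so a simple misprint is unlikely.

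**Joint check, assuming all five tests refer to the same order-averaged difference.** Let t_i be the signed root of each simple-effect F, so |t| = 2.241, 0.557, 1.503. Let s_i be the residual SDs of the three CBG–placebo differences, S their covariance matrix, V the sum of all its elements, and d_i = t_i s_i. Then

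- F_condition = (Σd_i)² / V
- F_interaction = [Σd_i² − (Σd_i)²/3] / [trace S − V/3]
- V cannot exceed (Σs_i)², reached when all correlations are 1.

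*Same sign, equal SDs.* (2.241 + 0.557 + 1.503)² = 18.50. With all correlations 1, V = 9 and F_condition = 18.50/9 = 2.06. With correlation 0.5, V = 6 and F_condition = 3.08. Reaching 1.19 needs V = 18.50/1.19 = 15.54, a mean correlation of (15.54 − 3)/6 = 2.09, which is impossible.

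*Same sign, any SDs and correlations.* F_condition = 1.19 now requires the SD-weighted mean of the t_i to be at most √1.19 = 1.09. That is possible only if T2, with the smallest t, carries much of the weight, and this limits the interaction. Over all SD ratios and all admissible V, the largest interaction F is about 2.2 (2.15 to 2.21 over the rounding ends tried), against 4.90 printed. The maximum lies near s = (0, 1, 1.294): Σd = 0.557 + 1.945 = 2.502, V = 6.26/1.19 = 5.26, and F_interaction = (4.094 − 2.087)/(2.674 − 1.754) = 2.18. If both targets may move, the closest same-sign pair is condition F about 1.68 with interaction F about 4.79; the exact point depends on how distance is weighted.

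*T2 opposite in sign.* Both printed values are met with ordinary SDs. Example: s = (1, 1.2324, 0.9476). Then d = (2.241, −0.686, 1.425), Σd = 2.979, V = 8.874/1.19 = 7.457 (allowed, since (Σs)² = 10.11), and F_interaction = (7.520 − 2.958)/(3.417 − 2.486) = 4.90. T3 opposite also fits, with more unequal SDs.

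**Relaxing the assumption.** If order enters uncentred, the test of a within-person effect is a test of the intercept, that is, of the difference at order = 0. Two constructions with 34 people, 17 per order:

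- Omnibus tests at order = 0, simple effects at the order mean: mean differences of −0.77, −0.19 and −0.52 (SD 2), all one sign, give all five printed values. This worked with 0/1 and with 1/2 coding, at correlations .3, .5 and .7.
- All five tests at order = 0: order-averaged differences of −0.5, −0.3 and −0.4, again one sign, give all five printed values under both codings. The mixed signs then belong to the intercept. Under 0/1 coding that is one sequence; under 1/2 coding it is an extrapolation to a group that does not exist.

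**Consequence for effect sizes.** Dividing t by √34 gives 0.38, 0.10 and 0.26 for stress at T1, T2 and T3, and √(3.25/34) = 0.31 for mood. This is valid only if the tests refer to the order mean. In a 17/17 design the intercept variance factor is 1/34 + x̄²/8.5. For 0/1 coding this is 1/34 + 0.25/8.5 = 2/34; for 1/2 coding it is 1/34 + 2.25/8.5 = 10/34. The variance at order = 0 is thus 2 or 10 times that at the mean.

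**The case against.** The strongest reply is that this is a reporting gap and no more. The results section refers to a published article for complete results, and the signs may be there. The plan does not forbid means after T0, and under the same plan the direction was given for anxiety and verbal memory. Mood is not significant on any test, so that hypothesis is unconfirmed whatever the sign. The section never claims that CBG lowered stress. All of this stands.

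A reader might go further and infer that CBG raised stress after the stress test, that the text conceals a reversal, or that a T1 benefit faded. The documents support none of these. The T1 effect itself has no printed sign. The T2 and T3 differences are not significant, and a change of sign there would not by itself rule out a decrease at T1. The reversal is also only one of two explanations: same-sign average effects reproduce every printed F when order is uncentred, even if all five tests used the same order value. Requiring one common order value is therefore not enough; that value must be the order mean.

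What the reply does not remove is that a primary result with a directional hypothesis is unsigned here, and that its F values leave open which effect was tested.

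**Conclusion.** The point holds in conditional form. Without any assumption, the stress and mood results are printed without direction, so a decrease in stress cannot be read from them. If all five stress tests refer to the same order-averaged difference in the same 34 people, one sign throughout is excluded by a wide margin (interaction F at most about 2.2 against 4.90), and rounding does not close the gap. So either the difference changes sign at T2 or T3 relative to T1, or some or all of the tests do not estimate the order-averaged CBG effect. Because the order coding is not stated, the documents do not show which. The standardised sizes, such as 0.38 at T1, should not be quoted as results until it is known that the tests refer to the order mean. Either way, the stress analysis as reported cannot answer its hypothesis.

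**What to change.** In the Data Analysis Plan: enter order centred or effect-coded, so that omnibus and simple-effect tests both refer to the average over the two orders. For anxiety, stress and mood, report from that one model the CBG minus placebo difference in change, in scale points with 95% CI, at T1, T2, T3 and averaged. Claim a decrease or an elevation only where the difference has the hypothesised sign.

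In Results (Primary Outcomes): state how order was coded and at what value each F was evaluated, rerun with centred order if it was not centred, and add the signed estimates for stress and mood.

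The cost is one rerun on existing data and a few lines of text. The printed F and p values may change, and the result may become less favourable.
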